6.10 Efficacy Analyses

6.10.1 Primary Efficacy Endpoints

The two primary efficacy endpoints will be tested hierarchically to maintain an overall one-sided alpha level of 0.025. Therefore, the test of resolution of symptoms based on the aggregate FLU-PRO Plus[©] symptom score will be performed only if the attainment of serum 25D levels \geq 50 ng/mL at Day 14 is significant at <0.025.

The first primary efficacy endpoint, attainment of serum 25D levels at ≥50 ng/mL, will be assessed with a Chi-square statistic at Day 14. The serum 25D levels will also be compared between treatment groups at Days 7, 21 and 28 with a Chi-square statistic.

The second primary efficacy endpoint is the number of days to resolution of symptoms, defined as a reduction in the aggregate FLU-PRO Plus[©] score for the selected five COVID-19 symptoms recorded on Day 0 (prior to study drug initiation) to or below 5 for a minimum of three consecutive days. The time to resolution is defined as the number of days from Day 1 (study drug initiation) to the first day of achieving the aggregate ≤5 score for a minimum of three consecutive days, provided that no score greater than 5 is recorded between the two qualifying scores. Resolution will be determined by the first two successive qualifying scores which span a minimum of three consecutive days. For clarity, resolution will be considered as having been achieved if two successive aggregate scores of ≤5 are recorded on the first day of this occurrence and on a subsequent day that is at least two days (but not more than 5 days) later even if no score has been recorded between the two days. Missing symptom score values will be handled as described in Section 6.2. The number of days to resolution will be analyzed with a Cox proportional hazards model with covariates (baseline aggregate FLU-PRO Plus[©] score for the selected five COVID-19 symptoms, baseline serum 25D, and body weight).

As a sensitivity analysis of the resolution of symptoms, a tipping point approach will be used starting with the analysis in which scores are available for three consecutive days, with no missing interval, followed by increasing numbers of missing days in the up to five-day interval, that is, 1, 2 and 3 missing days between the two consecutive qualifying scores.

Subgroup analyses for the primary efficacy endpoints will be based on age (\leq 40 or >40 years), severity of the selected five COVID-19 symptoms at baseline (aggregate FLU-PRO Plus[©] score of \leq or > the median score), attained serum 25D at Day 14 (below, within or above the targeted range of 50 to 100 ng/mL), body weight (\leq 100 or >100 kg), BMI (\leq 30 or >30), dosing compliance (<80% or \geq 80%), gender, race, ethnicity, number of comorbidities (<1 or \geq 1), duration of treatment (\leq 10 or >10 days) and prior or intercurrent COVID-19 vaccination and/or monoclonal antibody therapy for COVID-19.

In addition, the number of days to resolution of the five aggregated symptoms will be compared based on the serum 25D level at Day 14 (<50 ng/mL vs 50 to 100 ng/mL and 50 to 100 ng/mL vs >100 ng/mL), regardless of the assigned treatment group. The comparisons will be done using a Chi-square test. Frequency of relapses will be calculated, if possible, to account for potential worsening of symptoms after resolution (defined above), with relapse being defined as achieving an aggregate FLU-PRO Plus[©] score >5 for a minimum of three consecutive days.

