Data from Studies CTAP101-CL-1011, CTAP101-CL-1020 and 170074 show that an oral loading dose of 900 mcg of Rayaldee (CTAP101 Capsules) in the fasting state (approximately 25% BA) will raise serum 25D levels within ~9-12 hours by about 20-35 ng/mL, depending on the subject's body weight (the higher the body weight, the lower the expected increase in 25D). Many COVID-19 subjects are expected to have higher than normal body mass index (BMI) values in view of the latest reported US data. Each maintenance dose of Rayaldee (CTAP101 Capsules) (60 mcg/day) will increase serum 25D by another 0.6 ng/mL, as shown in Studies CTAP101-CL-3001, CTAP101-CL-3002 and CTAP101-CL-3003 [Sprague et al, 2016]. It follows that subjects having a baseline 25D level of ~25 ng/mL will reach ~45-60 ng/mL after the loading dose and ~59-74 ng/mL after 24 days of maintenance dosing. Subjects with slightly lower baseline levels of 25D will reach proportionately lower levels on treatment. There will be some subjects who have a higher baseline 25D level. For this reason, 25D levels will be checked at Days 7, 14 and 21 and dosing will be adjusted if levels exceed 100 ng/mL. FDA has approved Rayaldee (CTAP101 Capsules) to raise levels up to a target of 100 ng/mL in kidney patients (see APPENDIX 2.: Package Insert).

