3.3 Sample Size Calculation

Primary outcome #1 (attainment of serum 25D levels at ≥50 ng/mL): Assuming that no more than 25% of the control group will achieve an increase in serum 25D to ≥50 ng/mL by Day 28 versus greater than 75% in the CTAP101 Capsules group, a sample size of 19 per group will provide 90% power at one-sided alpha of 0.025 based on a Chi-square test of the two groups.

Primary outcome #2 (severity of illness by selected five COVID-19 symptoms): A sample size of 80 per group (total of 160) is planned. This will provide greater than 80% power at one-sided alpha of 0.025 based on a log rank test assuming 50% of subjects in the control group and 70% of the CTAP101 Capsules group will have achieved resolution of symptoms by Day 28. This is based on an expected hazard ratio (of achieving resolution) of 1.74.

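### Primary endpoint 1 (25D ≥50 ng/mL at Day 14) is analysed only by an unadjusted Chi-square: the gate is safe, but the effect size needs a baseline-adjusted estimate and a separate row for subjects below 50 ng/mL at entry

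*SAP*

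**What the plan says.** SAP 6.10.1 (and Protocol 9.10.1) states that the first primary endpoint "will be assessed with a Chi-square statistic at Day 14". The two primary endpoints are "tested hierarchically to maintain an overall one-sided alpha level of 0.025", so this test is the gate for symptom resolution. Under SAP 6.2, baseline 25D enters only as a predictor in the multiple imputation of missing 25D results, and each completed data set is again tested by Chi-square.

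The same section adjusts the Cox model for endpoint 2 for baseline symptom score, baseline 25D and body weight. SAP 6.10.2 uses baseline 25D and weight again in the logistic models for individual symptoms and mortality.

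On what drives the attained level, Protocol 3.2 puts the loading-dose rise at about 20-35 ng/mL, "depending on the subject's body weight (the higher the body weight, the lower the expected increase in 25D". It expects an average baseline of about 20-25 ng/mL, with the caveat that this may not hold, and adds: "There will be some subjects who have a higher baseline 25D level". Neither the entry criteria (Protocol 4.2, 4.3) nor the full analysis set (SAP 4.3) limits baseline 25D.

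SAP 3.3 plans for this endpoint on the assumption that "no more than 25% of the control group will achieve an increase in serum 25D to" the threshold (the time it states is Day 28), against more than 75% on active treatment. From these rates it derives 19 subjects per arm for 90% power at a one-sided 0.025 level.

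**The concern.** The outcome that baseline 25D and weight predict most directly is the one primary outcome analysed without them, and no reason is given. Protocol 5.3.4 describes 1:1 randomisation and names no stratification factor, so the design does not guard against a chance difference in baseline 25D either.

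There is a second, separate question of meaning. The planning text speaks of achieving an increase to the threshold, whereas the endpoint counts anyone at or above 50 ng/mL on Day 14, including subjects who were there on entry. The subgroup list in SAP 6.10.1 includes the 25D level attained at Day 14 but not the level at baseline, so no listed analysis shows how many of those who attained the level started there.

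At stake is the size of the biochemical effect on which the trial's hypothesis rests, not the pass/fail decision.

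**Working it through.** **1. The plan's own figure.** Inputs (SAP 3.3): p0 = 0.25, p1 = 0.75, one-sided alpha 0.025, power 90%.

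n = [1.960·√(2·0.5·0.5) + 1.282·√(0.25·0.75 + 0.75·0.25)]² / 0.5² = (1.386 + 0.785)² / 0.25 = 18.9, so 19 per group. Power at 19 is 0.902 (0.898 by exact enumeration). The stated figure reproduces.

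**2. Is the gate safe?** At 80 per arm: z = (0.50 − 1.960·√(0.5/80)) / √(0.375/80) = (0.500 − 0.155)/0.0685 = 5.04, so power exceeds 0.9999. With two thirds of the sample (53 per arm) it is still 0.9999. One-sided type I error at 80 per arm, with a common rate of 5% to 25%, is 0.021 to 0.026. The test is valid and heavily powered.

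**3. Precision gained by adjustment.** The documents give no SD for baseline 25D and none for the individual rise, so both are assumed. Simulation: 80 per arm, 2,000 trials per scenario, rise of 20-35 ng/mL by weight plus 10 maintenance doses × 0.6 = 6 ng/mL by Day 14 (Protocol 3.2), spread of the treated response SD 8 to 16. The unadjusted risk difference is compared with one standardised for baseline 25D and weight (linear and logistic working models).

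| Baseline mean, SD (ng/mL) | Share ≥50 at entry | Fall in variance |
|---|---|---|
| 22.5, 8 | 0% | 7-19% |
| 25, 10 | 0.6% | 8-22% |
| 25, 12, right-skewed | 4% | 17-27% |
| 30, 12, right-skewed | 6% | 19-30% |
| 37, 13 | 14-16% | 22-34% |
| 40, 15 | 25% | 30-40% |

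The lowest values in the first two rows come from the widest assumed spread (SD 16). With residual SD 6-9, a separate run gave 13-29% at a baseline mean of 22.5-25. A fair summary at the expected baseline is roughly 10-30%.

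At the planning rates the standard error is √(0.375/80) = 0.0685, a 95% half-width of 1.96 × 6.85 = 13.4 points. A 10% cut gives √(0.90) × 13.4 = 12.7 points; a 30% cut gives √(0.70) × 13.4 = 11.2 points.

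**4. Chance imbalance.** The SD of the between-arm difference in mean baseline is s·√(2/80): 1.26 ng/mL for s = 8 and 1.90 for s = 12. In simulation each 1 ng/mL moves the unadjusted difference by about 1.3-1.6 points. A two-SD imbalance therefore shifts the estimate by between 2 × 1.26 × 1.3 = 3.3 and 2 × 1.90 × 1.6 = 6.1 points.

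**5. Entrants already at ≥50 ng/mL.** Let q be their share. If they stay at ≥50 in both arms they contribute no difference, so D(below 50) = D(all)/(1 − q). This is an upper limit, because some placebo subjects will drift below 50.
- Planning rates, q = 20%: active (0.75 − 0.20)/0.80 = 0.688, control (0.25 − 0.20)/0.80 = 0.063, difference 62.5 points against 50, a gap of 12.5. For q = 5% and 10% the differences are 52.6 and 55.6.
- Expected baseline (mean 25, SD 10): 72.2/0.994 = 72.6, a gap of 0.4 points. With a right-skewed baseline and 4.1% at ≥50: 65.8/0.959 = 68.6, a gap of at most 2.8.
- Simulation with about 20% at ≥50: 68-72 points overall against 78-84 below 50.

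**The case against.** The strongest reply is that nothing decided by this test would change. The Chi-square is valid, power is above 99.99%, and dilution works against the sponsor. Chance imbalance is already covered by the error rate of a randomised comparison. The SAP names a test, not a risk difference, so precision might seem beside the point. All of this stands as far as the gate is concerned. It does not settle the estimate: SAP 2.2 defines the estimand as a difference between treatments in attainment, and that number will be reported and interpreted.

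A second reply also stands. Replacing the gate test would bring its own risk. In the roughly normal scenarios at the expected baseline, the simulated placebo rate is 0.1% to 1.6%, or about 0.1 to 1.3 events in 80 subjects, nearly all determined by baseline 25D. A plain logistic model could then fail through near-separation.

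A third is that high entrants should be few: the expected mean is 20-25 ng/mL, and Protocol 5.4 lists vitamin D supplements among therapies excluded at enrolment. That supports the small end of the dilution range. But Protocol 3.2 itself says the expectation may not hold.

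A reader might infer that the Chi-square is what makes high entrants count as attained. It is not. The endpoint definition does that, and an adjusted model would score them the same way. Only a restricted row shows the difference.

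**Conclusion.** The point holds as one of efficiency and interpretation, not of validity. Endpoint 1 lacks an adjusted estimate that the SAP's own covariates would supply. Under assumed SDs (baseline 8-12, residual 6-9), adjustment would cut the variance of the risk difference by roughly 10-30% at the protocol's expected baseline, and by up to about 40% if baseline levels were much higher. It would also remove most of a possible 3-6 point shift from chance imbalance in baseline 25D.

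Counting entrants already at ≥50 ng/mL costs under 1 point at the expected baseline if levels are roughly normal, 2-3 points if about 4-5% enter there, and about 10-13 points if about 20% do.

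Three stronger readings are not supported. A loss of about a third of the available precision needs baseline levels well above what the protocol expects, or SDs that the documents do not give. A threat to the gate or to type I error is contradicted by the power and error figures above. A loss concentrated in the weight and BMI subgroups is not borne out: at 20 per arm the relative gain from adjustment was 6-28%, no larger than overall.

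**What to change.** Leave the Chi-square at one-sided 0.025 as the gatekeeping test. Before unblinding, add to SAP 6.10.1:

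- **(a) Adjusted estimate.** A covariate-adjusted risk difference at Day 14 with 95% CI, from treatment, continuous baseline 25D and continuous body weight. Use a linear working model with robust standard error, or a standardised logistic model with a penalised fallback for sparse placebo events. Name the working model in advance. The raw proportions stay in the table.
- **(b) Supportive row.** Attainment by arm among subjects below 50 ng/mL at baseline, with the number per arm who entered at or above 50.

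Both can be extra rows in the planned attainment tables (14.2.1.1 and 14.2.1.2). The cost is SAP wording, a few lines of code and one more working model to specify. No new data are needed. Added after unblinding, the same analyses would be post hoc.

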4.2 Inclusion Criteria

Each subject must meet the following criteria to be enrolled and randomized into one of the two treatment groups of this study:

- 1) Male or female ≥ 18 years of age;
- 2) Confirmed within the past 3 days to have SARS-CoV-2 infection as evidenced by a positive nasopharyngeal swab test using RT-PCR or any substitutable FDA-authorized diagnostic test;
- 3) Confirmed to have only mild or moderate COVID-19 based on the first of the patient reported scores obtained during screening which meets the criterion of a FLU-PRO Plus[©] score ≥ 1.5 for each of the chest/respiratory and body/systemic domains, and the absence of clinical signs indicative of more severe disease (eg, oxygen saturation < 94% on room air or respiration rate >30 bpm);
- 4) Represents on self-assessment that the current COVID-19 symptoms are not consistent with usual health and that they are the same or worse than on the previous day;
- 5) Willing to limit the use of vitD therapies or supplements except for normally fortified food products (eg, milk) during the course of the 6-week study;
- 6) Must demonstrate the ability to comply with all study requirements; and,
- 7) Must be without any disease state or physical condition that might impair evaluation of safety or which, in the investigator's opinion, would interfere with study participation.

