6.2 Medical History and Concomitant Medications

A medical history, including demographics and concomitant medications, will be recorded at the screening visit (Visit 1). Any symptom related to COVID-19 that started prior to initial dose, does not need to be reported as medical history. Concomitant medications will be recorded at each additional study visit.

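### The primary Cox model omits age and pre-Day-1 vaccination or antibody therapy, which the plan uses only as subgroup factors; adding both before unblinding may recover some power at almost no cost.

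*SAP*

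**What the plan says.** The second primary endpoint, days to resolution, is analysed with a Cox model adjusted for the baseline aggregate score for the "selected five COVID-19 symptoms, baseline serum 25D, and body weight" (SAP 6.10.1; Protocol 9.10.1 has the same three covariates). Age, split at 40 years, is a subgroup factor in the same SAP section, and so is "prior or intercurrent COVID-19 vaccination and/or monoclonal antibody therapy for COVID-19". Neither enters the model. Protocol 5.3.4 describes 1:1 allocation from a computer-generated code and names no stratification factors.

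The timing rule at entry concerns the test: "Confirmed within the past 3 days to have SARS-CoV-2 infection as evidenced by a positive nasopharyngeal swab test" (Protocol 4.2). Days since symptom onset is not an entry limit, a listed baseline variable, a subgroup factor or a covariate. Protocol 6.2 adds: "Any symptom related to COVID-19 that started prior to initial dose, does not need to be reported as medical history".

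For size, SAP 3.3 states: "A sample size of 80 per group (total of 160) is planned". On power it says: "This will provide greater than 80% power at one-sided alpha of 0.025 based on a log rank test". The resolution rates assumed at Day 28 are 50% on placebo and 70% on active drug, and the section gives the matching effect size: "This is based on an expected hazard ratio (of achieving resolution) of 1.74".

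**The concern.** Omitting a prognostic baseline covariate from a Cox model pulls the treatment hazard ratio toward 1 and leaves chance imbalance in that covariate uncorrected. With no strata described, the model is the only described protection against such imbalance. Age and prior protection are plausible predictors of recovery time, and the plan treats both as important enough for subgroup analysis. At stake is power on the symptom endpoint, where the stated Day 28 inputs leave little to spare.

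**Working it through.** **1. The plan's own figure.** Inputs are from SAP 3.3: 80 per group, 50% v 70% resolved by Day 28, HR 1.74, one-sided alpha 0.025.

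- HR under exponential times: ln(0.30)/ln(0.50) = 1.737, which agrees with 1.74.
- Expected events: 80 × 0.50 + 80 × 0.70 = 40 + 56 = 96.
- Schoenfeld power: Φ(√96/2 × ln 1.74 − 1.960) = Φ(2.714 − 1.960) = Φ(0.754) = 77.4%. A simulated log-rank test gives 77.3%.
- SAP 5.2 reports that more than 92% of dosed subjects had a baseline score above 5 and so stay in the full analysis set. At 92%, events are 96 × 0.92 = 88.3 and power is 74.0%.

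The stated figure of more than 80% is therefore not reached on the Day 28 inputs. If events to Day 42 counted, at constant hazard, there would be 118.6 events and power of 85.4%. This matters here only as a measure of headroom.

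**2. Effect of adding covariates.** The documents give no prognostic strengths, so every strength below is an assumption. Design: 160 subjects, daily times, censoring at Day 28, conditional treatment HR 1.74. The planned model includes the baseline score (assumed HR 0.7 per SD, independent of the other factors) but not 25D or body weight. There were 1,000 trials per scenario, so each figure has a standard error of about √(0.75 × 0.25/1000) = 1.4 points.

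| Assumed HR: vaccination; age per SD; onset per SD | Planned model | + vaccination and age | + onset as well | Gain from the first two |
|---|---|---|---|---|
| None prognostic | 75.9% | 76.5% | 75.7% | 0.6 |
| Moderate: 1.5; 0.8; 1.25 | 71.3% | 74.6% | 75.9% | 3.3 |
| Strong: 2.0; 0.7; 1.5 | 64.7% | 71.1% | 76.7% | 6.4 |

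A separate run of the same kind, rounded to whole points, gave for the planned model and then with vaccination and age:

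- none: 75 to 76% (gain 1)
- weak: 77 to 78% (gain 1)
- moderate: 73 to 75% (gain 2)
- strong: 65 to 72% (gain 7)

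**3. Correlated score.** If the baseline score is correlated with the other factors, it already carries part of their information. The gain from vaccination and age is then 73.5 − 71.5 = 2.0 points (moderate) and 70.7 − 66.4 = 4.3 points (strong).

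**4. Holding 50% v 70% fixed.** This keeps the sizing assumption as the plan states it. These runs used 4,000 trials and had no baseline score in the model. Power without and with vaccination and age was:

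- none: 75.6 and 75.7%
- weak: 75.2 and 76.0%
- moderate: 75.8 and 78.2%
- strong: 78.0 and 83.7%

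The gains are 0.1, 0.8, 2.4 and 5.7 points. The model without these covariates stays at 75 to 78% throughout.

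**The case against.** **The covariates are pre-specified and the test is valid.** This stands. Either model keeps its type I error under randomisation, and age and vaccination are examined as subgroups. The point is about efficiency only.

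**The plan is not unadjusted.** This also stands: the fair comparator includes the baseline score, as in steps 2 and 3. A gain remains, but a smaller one when the score is correlated with the other factors. Vaccination alone adds little: in one run with vaccination HR 1.5, power went from 74.1% to 74.8%.

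**The sizing assumption is not eroded.** Correct. The HR of 1.74 comes from marginal rates and an unadjusted log-rank test. Step 4 shows that omission forgoes a possible gain and does not lower power below the planned level.

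**Vaccination may not be fully captured.** This stands in part. Age is certainly collected (SAP 6.7). For vaccination, collection is inferred from its use as a subgroup factor. The medication history covers three months (Protocol 6.8 and 7.1.1) or 12 weeks (SAP 6.8), so earlier doses could be missed.

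**A stronger reading about symptom onset.** A reader might infer from Protocol 6.2 that sites are told not to record when symptoms began. The sentence only waives reporting pre-dose COVID-19 symptoms as medical history, and the case report form is not among the documents. Entry also does more than date the test. Protocol 4.2 requires symptoms the same as or worse than the day before and a minimum score in two domains, which narrows the spread in illness stage without capping days since onset.

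**Conclusion.** The omission is real and cheap to repair. Its size depends on strengths the documents do not give: about 0 to 1 point of power if age and prior vaccination or antibody therapy are not or only weakly prognostic, 2 to 3 if moderate, and 6 to 7 if strong, falling to about 4 in the strong case if they are correlated with the baseline score. If they are not prognostic, the change is within simulation error. These figures assume proportional hazards, censoring at Day 28, half the subjects vaccinated and complete covariate data.

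A reader might go further and say that the plan loses power as a matter of fact, or that its primary test is biased. The documents support neither: the power gain is conditional on prognostic strength, and type I error is not affected.

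**What to change.** Before unblinding, amend SAP 6.10.1, and Protocol 9.10.1 to match:

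- Add age (continuous) and COVID-19 vaccination and/or monoclonal antibody received before Day 1 (yes/no) to the primary Cox model.
- Use the same covariates in a Cox model for the first secondary endpoint. SAP 6.10.2 names no model for that endpoint, so name it there.
- Derive the indicator from pre-Day-1 data only. The SAP's subgroup variable pools prior with intercurrent exposure, and the intercurrent part is post-baseline.
- Confirm, while still blinded, that vaccination earlier than the three-month look-back is captured.
- Leave the mortality logistic model unchanged. SAP 6.10.2 already allows for too few deaths to analyse.

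Symptom onset need not enter the primary model. If onset dates are held in source, days from onset to Day 1 can be a covariate in a supportive sensitivity analysis, with a stated rule for missing dates.

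The cost is SAP wording and two parameters. The model goes from four terms to six against about 88 to 96 events, or 88/6 ≈ 15 to 96/6 = 16 events per term. SAP 6.2 describes the study as ongoing with blinded data, so the change can still be pre-specified.
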